- Can speak/read English or Spanish
- Have access to a Zoom-capable device
- Able to attend first study session within 2 weeks of survivor's screening
- Are in contact with the survivor at least once a week
- In the opinion of the survivor, are able to make an independent decision about whether or not to participate in the study
- Have a way to receive survey links and complete surveys privately (i.e., without potential device or account access by the survivor)

Exclusion criteria

Exclusion Criteria (Survivors):

- Active psychosis
- Active suicidal intent

Exclusion Criteria (Supporters):

- Perpetrated the sexual assault
- Engaged in severe past-year violence or abuse (as defined by the survivor) against the survivor
- The survivor has not told the supporter about the sexual assault at the time of screening and was not already planning to tell the supporter
- In the opinion of the survivor, relational conflict exists between the survivor and supporter that potentially could be exacerbated by program participation

Eligibility criteria for study centers (if applicable)

N/A

Eligibility criteria for individuals who will perform the interventions

The intervention will be delivered by either the principal investigator (a licensed clinical psychologist) or a staff member trained by the principal investigator

11. Interventions

11a. Interventions for each group with sufficient detail to allow replication, including how and when they will be administered

Intervention

Both telehealth sessions will be 90 min and will be delivered using a slide deck and a script. Sessions will be audio recorded for supervision and fidelity tracking. Clients will be sent an electronic and/or paper workbook following session 1. The clinician will complete a clinical note regarding content coverage and clinical observations. In session 2, the note will document attendance, homework completion, and skills practice. We will also assess homework completion and skills practice via survivor and supporter self-report at 1-month follow-up.

Dyadic CARE

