Dyadic CARE involves two telehealth sessions with a clinician, the survivor, and a supporter of the survivor's choice. Session content uses cognitive-behavioral strategies (e.g., encouraging non-avoidance) to encourage communication and improve supporters' responses in trauma-related conversations. Between sessions, both the survivor and the supporter are instructed to review session content and have guided discussions with the assistance of a workbook.

Supporter-Only CARE

Supporter-only CARE involves two telehealth sessions with a clinician and a supporter of the survivor's choice, without the survivor present. Session content uses cognitive-behavioral strategies (e.g., encouraging non-avoidance) to

encourage communication and improve supporters' responses in trauma-related conversations. Between sessions, both the survivor and the supporter are instructed to review session content and have guided discussions with the assistance of a workbook.

Comparison

Waitlist Control

After completing baseline, participants will be invited to schedule a CARE session in 3 months (i.e., after the completion of all study assessments). The version of CARE received at that point will be selected by the survivor.

Participants will complete self-report assessments at post-session-1, Month 1, Month 2, and Month 3.

11b. Criteria for discontinuing or modifying allocated interventions for a given trial participant

Participants who withdraw consent for participation will no longer be contacted by study staff or sent automated reminders to complete study tasks.

Participants will be withdrawn from the research if at any point if it becomes known that a participant does not meet eligibility criteria for the study, if a participant's condition deteriorates, or if it becomes known that they require a higher level or different type of care that is incompatible with study participation. If this occurs, participants will be asked to withdraw from the study and appropriate referrals will be made.

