Once enrolled, both survivors and supporters may choose to opt out of all study questionnaires and still receive the intervention, although they will not be paid for questionnaires. Survivors and supports are permitted to individually withdraw without affecting the eligibility of the other participant (i.e., if a survivor withdraws or cannot be reached, the supporter may still receive the intervention and be paid for questionnaires), but the survivor participant may request to withdraw both themselves and their supporter from the study at any time.

11c. Strategies to improve adherence to intervention protocols, and any procedures for monitoring adherence

All assessments will occur via online self-report surveys. These will be auto-generated from our secure online system, and participants will receive reminders from the clinician within one week of not completing surveys, to remind participants to submit their answers. Survivors and supporters will be paid \$10, \$10, \$20, \$30, and \$40 for baseline, post-session-1, 1-month, 2-month, and 3-month assessments, respectively (total possible per person: \$110). Participants may choose to be paid via preloaded debit card or emailed gift card.

Staff will do weekly checks and audits of all study interactions & documentation to ensure protocol adherence.

11d. Relevant concomitant care and interventions that are permitted or prohibited during the trial

[figure not shown]
Participants will not be restricted from accessing any care or interventions during the course of the trial. It is likely that individuals recruited from the Harborview Abuse and Trauma Center and other key recruitment sites will receive treatment for sexual-assault-related distress while enrolled in the study.

12. Outcomes

See ClinicalTrials.gov

13. Participant timeline

(A schematic diagram is highly recommended)

14. Sample size

Estimated number of participants needed to achieve study objectives

60-72 dyads (120-144 participants)

How sample size was determined

Including clinical and statistical assumptions supporting any sample size calculations

As this is a pilot trial, the sample size was selected primarily for feasibility rather than significance testing.

15. Recruitment

Recruitment sites and procedures; site-specific and general strategies for achieving adequate participant enrollment to reach target sample size

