All assessments will occur via online self-report surveys. Survey invitations and reminders will be sent via email or text message. Participants will complete follow-up questionnaires after session 1 and at 1, 2, and 3 months post-baseline to assess changes in knowledge, disclosure, and symptoms. We selected these time points because recovery occurs most rapidly within the first 3 months post-assault ([name] et al., 2021).

Survivors and supporters will be paid \$10, \$10, \$20, \$30, and \$40 for baseline, post-session-1, 1-month, 2-month, and 3-month assessments, respectively (total possible per person: \$110). Participants may choose to be paid via preloaded debit card or emailed gift card and will be provided with referrals.

18b. Plans to promote participant retention and complete follow-up

List of any outcome data to be collected for participants who discontinue or deviate from intervention protocols

The following steps will be taken to promote retention:

- We will collect extensive contact data from participants and attempt to reach them for all follow-up assessments unless directed otherwise.
- Participants will receive text, email, and/or phone call reminders to complete the study surveys.
- Survivors and supporters will be paid \$10, \$10, \$20, \$30, and \$40 for baseline, post-session-1, 1-month, 2-month, and 3-month assessments, respectively (total possible per person: \$110). Participants may choose to be paid via preloaded debit card or emailed gift card.
- The study clinician will emphasize the importance of completing study surveys.
- The study clinician will instruct participants to complete the post-intervention survey once they terminate the initial CARE appointment.

19. Data management

Plans for data entry, coding, security, and storage

Including any related processes to promote data quality (eg, double data entry; range checks for data values). Reference to where details of data management procedures can be found, if not in the protocol.

Entry and coding

Data will be completely digital; no data entry will be needed. In some cases, scale scores will be automatically calculated by custom programming. When this does

not occur, study staff will create SPSS syntax and a data dictionary referencing scoring procedures.

Security and storage

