Reference to where other details of the statistical analysis plan can be found, if not in the protocol

Analyses will be conducted with the intent-to-treat sample. As this study is not powered to detect statistical significance, we will examine the direction and magnitude of effects to preliminarily understand efficacy and test significance in an exploratory manner only. Within-group ds will be calculated as the mean-level difference in scores from baseline to follow-up for each condition divided by the standard deviation of change scores. Between-group ds will represent relative change between conditions and will be calculated as the difference between within-group ds.

Acceptability (H1)

We will use descriptive statistics to summarize acceptability ratings among dyads randomized to dyadic or supporter-only CARE. We will use independent-samples t-tests and between-group *ds* to compare acceptability by condition.

Efficacy (H2–4)

We will calculate within- and between-group *ds* to represent mean changes on focal outcomes. We will use the reliable change index to quantify whether change is unlikely to be attributable to measurement error, and we will report odds ratios for differences in percent with reliable improvement by condition. We will also report the percent of participants meeting diagnostic criteria based on the PCL at baseline and 3-month follow-up.

Paired sample t-tests will evaluate mean changes from baseline to follow-up. We will test time-by-condition interactions in random-effects models using maximum likelihood estimation to account for missing data. We will test covariates including relationship type, study clinician, participant age, and prior assault history. We will conduct sensitivity analyses with English and Spanish-language participants separately.

20b. Methods for any additional analyses

(eg, subgroup and adjusted analyses)

We will test moderation and visually examine results across groups as a function of:

- Baseline PTSD severity and PCL score \geq cutoff of 33
- Relationship type (friend, parent, partner, other)
- Caregiver burden (Impact on Friends - Ineffectiveness Subscale)

We will conduct sensitivity analyses in the following samples:

- English speakers only

20c. Analysis population and missing data

Definition of analysis population related to nonadherence (eg, as randomized analysis), and any statistical methods to handle missing data (eg, multiple imputation)

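### Section 11b withdraws participants who deteriorate from the research, not only from CARE, and nothing expressly keeps their surveys going, so some month-3 PTSD and stress data may be lost for reasons related to the outcome.

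*Combined protocol and SAP*

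**What the plan says.** Section 11b is headed as criteria for stopping or modifying the allocated intervention, but its rule concerns the study as a whole: "Participants will be withdrawn from the research if at any point" one of three things happens. The participant is found to be ineligible, deteriorates, or needs care incompatible with participation. The second and third triggers read "condition deteriorates, or if it becomes known that they require a higher level or different type of care". The action is that "participants will be asked to withdraw from the study and appropriate referrals will be made". A separate sentence in 11b ends contact and reminders for those who withdraw consent. 11b also lets participants skip questionnaires and keep CARE, but gives no reverse option.

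Section 18b carries the template prompt "List of any outcome data to be collected for participants who discontinue or deviate from intervention protocols". Its answer is a list of general retention steps, including to "attempt to reach them for all follow-up assessments unless directed otherwise". People withdrawn under 11b are not mentioned.

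Section 20a states that "we will examine the direction and magnitude of effects to preliminarily understand efficacy". It names maximum likelihood for the random-effects models only. No missing-data handling is given for the ds, paired t-tests, reliable-change rates or percentages meeting PCL criteria. Section 20c specifies analysis as randomised, with all participants' outcome data included.

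**The concern.** H4 compares survivor PTSD and stress at 3 months with waitlist. A rule that ends participation when a survivor gets worse selects on an early version of that outcome. If the surveys stop too, the month-3 data come from a group with some of its worst courses removed. The summaries with no missing-data method would then describe those who remained, and in this pilot the direction and size of those summaries are the main efficacy output. Section 22 also relies on longitudinal symptom measures for safety, so the same loss would thin the harm data.

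The waitlist arm shows why scope matters. Its CARE session comes only after all assessments, so during the three months there is little besides the surveys for withdrawal to end.

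**Working it through.** **Text.** 11b withdraws people from the research. 18b promises general effort at follow-up without saying that it reaches those withdrawn. 20c governs how collected data are analysed, not whether collection continues. No sentence separates stopping CARE from stopping assessments for this group.

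**Inputs.** From the plan: 60-72 dyads (section 14) allocated 1:1:1, so 60/3 = 20 to 72/3 = 24 survivors per arm. The plan gives no withdrawal rate, SD or correlation, so the rest is assumed: early and month-3 change each N(-8, SD 12), negative meaning improvement; correlation r between them of 0.2-0.6; a 10-point cut for reliable change.

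**How many could be affected.** P(early worsening of 10 or more) = P(Z > (10 + 8)/12 = 1.5) = 6.7%, or 20 × 0.0668 = 1.3 to 24 × 0.0668 = 1.6 survivors per arm. The third-worst survivor worsens on average by only 5.6 (n = 20) or 6.9 (n = 24) points. One or two lost per arm is therefore the relevant range; three would include people short of the cut.

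**Within-group effect.** If the k survivors with the worst early change lose month 3, the mean month-3 change of the rest is overstated by r × 12 × (sum of the k largest expected normal order statistics)/(n − k). The two largest are 1.867 and 1.408 at n = 20, and 1.948 and 1.503 at n = 24.

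- k = 1: lowest 0.2 × 12 × 1.948/23 = 0.20 points; highest 0.6 × 12 × 1.867/19 = 0.71.
- k = 2: lowest 0.2 × 12 × 3.451/22 = 0.38; highest 0.6 × 12 × 3.275/18 = 1.31.

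Simulation (100,000 arms per setting) gives the same means. On the plan's definition (mean change over SD of change), within-group d moves from about -0.69 to between -0.71 and -0.78 (k = 1) or between -0.73 and -0.85 (k = 2). The share improving by 10 or more rises from 43.4% to 44-45% or 45-47%. With r = 0, for example if referral removes the carry-over, the effect is about zero.

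**Between-group effect, rule used in one arm only.** With no true effect, the plan's between-group d shifts by 0.02-0.16 in favour of whichever arm lost its worst cases. The standard error is sqrt(2 × (1/n + d²/(2n))) with d = -0.67, which is 0.35 at n = 20 and 0.32 at n = 24. The largest shift is thus 0.16/0.35, about 0.45 of one standard error.

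**Between-group effect, same rule in both arms, CARE effective.** Assume waitlist change -8, CARE change -14, SD 12, r = 0.6, and everyone worsening by 10 or more lost. The shift is 0.6 × 12 × φ(z)/Φ(z).

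- Waitlist: z = 1.5, 6.7% lost, shift 7.2 × 0.1295/0.9332 = 1.0 point.
- CARE: z = (10 + 14)/12 = 2, 2.3% lost, shift 7.2 × 0.0540/0.9772 = 0.4 points.
- The true 6-point benefit appears as about 5.4, understated by 1.0 − 0.4 = 0.6.

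**Likelihood model.** If a completed survey recorded the worsening that led to withdrawal, the model's bias is essentially zero. If the worsening was not recorded but a completed survey correlates 0.5, 0.7 or 0.9 with it, the bias at n = 20, k = 2, r = 0.6 falls from about 1.3 to about 0.7, 0.4 and 0.2 points (the survey also correlating 0.6 with month 3).

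**The case against.** The strongest reply is that the plan already covers this. 11b sits under an intervention heading; participants are only asked to withdraw, so they may decline; the no-contact sentence applies to withdrawn consent; 18b commits staff to all follow-ups unless told otherwise; and 20c keeps everyone as randomised. All of that is accurate. It shows that data loss is one reading of an unclear text and not a settled intention. It does not supply the missing statement, because 18b leaves unanswered its own prompt about people who discontinue, and a general retention step does not plainly override withdrawal from the research.

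A second reply is that use will be rare. This largely stands. Section 11d says "Participants will not be restricted from accessing any care or interventions during the course of the trial", so outside treatment alone does not trigger the rule, and section 21b meets very high symptom levels with additional resources.

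A reader might infer two stronger things. One is that the plan abandons follow-up of everyone who worsens; the wording does not go that far. The other is that the rule flatters CARE. The documents do not show that it is applied more in one arm, since surveys and symptom monitoring run in all three. Unequal detection is possible, because only dyadic CARE brings survivors into sessions during follow-up, but the direction is not established.

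**Conclusion.** The point holds as a minor defect of wording with a possible statistical consequence. Following 11b literally can remove month-3 H4 data informatively. The likely result is some overstatement of within-group improvement in the summaries without missing-data handling; the likelihood model reduces this to the extent that completed surveys recorded, or correlate with, the worsening. Between-group bias has no fixed sign: unequal use could favour either arm, equal use with no true effect gives about none, and equal use with an effective CARE works against it.

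Every magnitude shown rests on assumed change scores, correlations and counts; none can be derived from the documents. The shifts are small against the imprecision of 20-24 per arm, and the trial is an exploratory pilot. Confidence is medium, mainly because the frequency of use is unknown.

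**What to change.** Amend 11b and 18b so that deterioration, or a need for other care, stops or modifies CARE and triggers referral, while the month 1, 2 and 3 surveys continue where clinically safe and unless the participant declines or withdraws consent. Leave the ineligibility clause unchanged, so that, for example, a supporter found to meet the exclusion "Perpetrated the sexual assault" is still removed completely. Analyse as randomised and report withdrawal reasons by arm and time.

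If data have already been lost this way, add one sensitivity analysis counting those withdrawn for deterioration as not reliably improved. Under the assumptions above, with one or two lost, it gives 40-43% against a true 43.4%. Present it as a conservative check, not a guaranteed bracket: if referral made withdrawn survivors do better than those who stayed, both it and the completers' rate could fall below the truth.

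The cost is one amendment with PI and IRB approval (section 25). Surveys are automated, and payments for months 1-3 are at most $20 + $30 + $40 = $90 per person, within the planned $110. The real downside is survey burden on distressed participants, some as young as 14, and a case-by-case clinical judgment on whether continued surveys are safe. If the sponsor always meant surveys to continue, the amendment simply says so.

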This pilot randomized clinical trial uses a unmasked, prospective, parallel group, superiority design.

Participants are allocated 1:1:1 (unstratified) to dyadic CARE, supporter-only CARE, or waitlist control. Assessments are completed via self-report at baseline, post session 1, and 1, 2, and 3 months postbaseline.

7. Objectives

(Specific objectives or hypotheses)

The goal of this protocol is to describe our methods for a pilot randomized clinical trial of dyadic and supporter-only CARE. Our goals are to understand feasibility, acceptability, and preliminarily characterize efficacy. We hypothesize:

H1: Dyadic and supporter-only CARE will be rated as acceptable by survivors and supporters at 1-month follow-up.

H2: Dyadic and supporter-only CARE will lead to increases in survivor and supporter knowledge from baseline to 1-month follow-up.

H3: Dyadic and supporter-only CARE will improve disclosure experiences (i.e., increasing survivor disclosure frequency, reducing supporter negative reactions, increasing supporter responsiveness) at 1-month follow-up compared to waitlist.

H4: Dyadic CARE and supporter-only CARE will improve functional outcomes among survivors (i.e., PTSD, stress, relationship quality) and supporters (i.e., stress, relationship quality) at 3-month follow-up compared to waitlist.

8. Description of trial design

Type of trial

(eg, parallel group, crossover, factorial, single group)

Parallel group, three arm

Allocation ratio

1:1:1

Framework

(eg, superiority, equivalence, noninferiority, exploratory)

Superiority

Methods: Participants, Interventions, and Outcomes

9. Study setting

Description of study settings

Remote

Reference to where list of study sites can be obtained

N/A

10. Eligibility Criteria

Inclusion criteria

Inclusion Criteria (Survivors):

- Age 14+ years
- Can speak/read English or Spanish
- Have access to a Zoom-capable device
- Screened for eligibility within 10 weeks of sexual assault, defined as any unwanted, distressing sexual contact (e.g., unwanted touching, coerced sexual activity, rape)
- Able to attend first study session within 2 weeks of screening
- Elevated PTSD symptoms at screening as operationalized by a Primary Care PTSD Screen score of 2/5 or above
- Able to identify an eligible supporter
- Have a way to receive survey links and complete surveys privately (i.e., without potential device or account access by the supporter)

Inclusion Criteria (Supporters):

- Age 14+ years

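### Section 20a's change ds carry no small-sample correction: at an expected 20–24 pairs per arm, within-group ds are inflated in magnitude by about 3.4–4.2%, and between-group ds can shift either way if completers differ

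*Combined protocol and SAP*

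**What the plan says.** Section 20a gives an explicit formula. For the numerator: "Within-group ds will be calculated as the mean-level difference in scores from baseline to follow-up for each condition". For the denominator: "divided by the standard deviation of change scores". Between-group ds "will be calculated as the difference between within-group ds". Neither 20a nor any other section mentions a small-sample (Hedges) correction.

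The same section makes these ds a main reading of efficacy: "we will examine the direction and magnitude of effects to preliminarily understand efficacy". Significance tests are exploratory only.

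On numbers, Section 14 plans 60–72 dyads and says "the sample size was selected primarily for feasibility rather than significance testing". The trial-design description states: "Participants are allocated 1:1:1 (unstratified) to dyadic CARE, supporter-only CARE, or waitlist control". Section 16a repeats that there is no stratification, and blocking is not mentioned. No attrition rate is given. Maximum likelihood is named for the random-effects models, but no missing-data rule is given for the ds.

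For H1, Section 20a also uses t-tests and between-group ds "to compare acceptability by condition". Section 7 places that rating at 1 month, with no baseline value described.

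**The concern.** A mean divided by a sample SD overstates the true standardised mean in small samples, because the reciprocal of an estimated SD is on average too large. The factor depends only on the degrees of freedom of the SD. Each arm's d uses that arm's own SD on n − 1 degrees of freedom, so each arm has its own inflation factor.

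That matters slightly more here than in a trial judged by a test. The pilot reads efficacy from the size of d, and all arms are expected to improve: the background text describes natural recovery as common, and Section 18a says recovery is fastest in the first three months. The factor therefore multiplies each arm's whole change, natural recovery included, and not only the part due to CARE. If arms end with different numbers of completers, the factors do not match and the difference between ds is distorted.

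**Working it through.** **Inputs from the documents.** 60–72 dyads (Section 14); three arms at 1:1:1 (Section 8). 60/3 = 20 and 72/3 = 24, so 20–24 survivors and 20–24 supporters per arm are expected. A pair here is one person's baseline and follow-up score. Section 14's participant counts agree: 60 × 2 = 120 and 72 × 2 = 144. There is no power or effect-size figure to reproduce.

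**Assumptions.** Change scores are normal. The ds are computed separately for survivors and supporters, as H4's outcomes by role suggest. All completer counts below 20–24, and all true ds, are illustrative.

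**Formula.** For a within-group d with df = n − 1, the expected value is δ/J, where J = Γ(df/2) / [√(df/2) Γ((df − 1)/2)], approximately 1 − 3/(4 df − 1). For n = 20 the approximation gives 1 − 3/75 = 0.960; for n = 24, 1 − 3/91 = 0.967.

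**Within-group d.**

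| n | J (exact) | Inflation, 1/J − 1 |
|---|---|---|
| 24 | 0.9670 | 3.4% |
| 22 | 0.9638 | 3.8% |
| 20 | 0.9599 | 4.2% |
| 15 (assumed) | 0.9453 | 5.8% |
| 12 (assumed) | 0.9300 | 7.5% |

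Simulation (200,000 normal samples per setting, true d = 0.8) gave mean ds of 0.834 at n = 20 and 0.827 at n = 24, which agrees with the formula.

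**Between-group d, equal completers.** True 0.8 and 0.5 (difference 0.30): expected 0.313 at 20 per arm and 0.310 at 24, the same 4.2% and 3.4%.

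**Between-group d, unequal completers (CARE listed first).**
- True 1.2 and 0.8, 15 versus 22: 1.2/0.9453 − 0.8/0.9638 = 0.439, against 0.40 (+10%).
- The same true ds, 22 versus 15: 1.2/0.9638 − 0.8/0.9453 = 0.399, essentially no bias.
- True 0.8 and 0.7, 20 versus 14: 0.090, against 0.10 (downward).
- Equal true ds of 1.0: 1/0.9453 − 1/0.9638 = +0.02 with 15 versus 22, and −0.02 with 22 versus 15.

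**H1 acceptability d.** There is no change score. If a pooled SD is used (assumption), df = 2n − 2, which is 38 or 46, and the inflation is 2.0% or 1.7%.

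**Against sampling error.** At a true within-group d of 0.8 the bias is 0.034 with a standard error of 0.277 (n = 20), or 0.027 with 0.249 (n = 24): about 0.12 and 0.11 standard errors. For the 0.439 example, using var(d) ≈ 1/n + d²/(2n), the standard error is √(0.1147 + 0.0600) ≈ 0.42, and 0.039/0.42 ≈ 0.09.

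**Effect of the correction.** At n = 20 and true d = 0.8, the uncorrected mean squared error is 0.277² + 0.034² ≈ 0.078. After multiplying by 0.960 the bias is gone and it is (0.960 × 0.277)² ≈ 0.071. Bias and variance both fall.

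**The case against.** The strongest objection is that this changes no conclusion. The bias is about a tenth of a standard error, no decision rule depends on d, the sample was set for feasibility, and efficacy is called preliminary. The formula is a standard one, openly stated, and a reader given completer counts could apply J. Section 20a also reports reliable change with odds ratios, the percentage meeting PCL diagnostic criteria, and random-effects models, none of which carries this bias. J is exact only under normality, which outcomes such as disclosure frequency may not satisfy, and it leaves each arm's d divided by its own SD. All of this stands. It sets the priority low, but it gives no reason to keep the uncorrected estimator.

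A reader might infer three stronger claims that the documents do not support:
- *That every reported d is biased upward by 3–4%.* The inflation is proportional and away from zero: nil where true change is nil, and it makes worsening look worse. The acceptability d is inflated by only about 1.7–2.0% on a pooled SD. A between-group d can be biased downward.
- *That the bias favours CARE.* That needs CARE to have fewer completers than waitlist. Nothing in the documents says so, and reversing the counts removes or reverses the effect.
- *That 20–24 is the largest an arm can be.* It is the expected size. If randomization is simple, the central 95% range for one arm is 13–27 of 60 or 16–32 of 72.

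**Conclusion.** The point holds as a minor, free improvement. Section 20a states an uncorrected estimator and nothing elsewhere corrects it. At the expected arm sizes, within-group change ds are too large in magnitude by about 3.4–4.2% under normality, and by more after dropout. Between-group change ds inherit that proportion when completers are equal. When completers differ, the distortion may go either way, and the ±0.02 seen at equal true ds of 1.0 shows that it need not vanish when there is no true difference. The percentages at full follow-up rest on the documents' sample size and on normality. Those after dropout, and every unequal-completer example, rest on assumed counts. The finding does not call the design or the pilot's main conclusions into question.

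**What to change.** Add to Section 20a, in substance: each within-group d will be multiplied by J = 1 − 3/(4 df − 1), where df is the number of pairs contributing to that arm's SD of change minus 1; between-group ds for change outcomes will be differences of these corrected values; the number of pairs contributing in each arm will be reported beside each d.

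For H1, state the denominator of the acceptability d. If it is a pooled SD, use the two-sample df (the two arms' completers minus 2) in the same formula.

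The cost is a few lines of SAP text and one multiplication per d, with no new data and no change to the design. Reported effects will be slightly smaller. For clearly non-normal outcomes the correction is approximate, and the text should say so.

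### For H2–H4, the between-group d in 20a is scaled by the SD of change scores, so its size depends on the baseline-to-follow-up correlation as well as on the benefit, and it is not directly comparable with an ordinary standardised mean difference.

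*Combined protocol and SAP*

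**What the plan says.** Section 20a defines the within-group d as the mean change from baseline to follow-up "for each condition divided by the standard deviation of change scores". It continues: "Between-group ds will represent relative change between conditions and will be calculated as the difference between within-group ds". No other standardiser is named. Under the efficacy heading of 20a (H2–H4), within- and between-group ds are to be calculated "to represent mean changes on focal outcomes".

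The ds carry weight because the study is described as not powered for significance: "we will examine the direction and magnitude of effects to preliminarily understand efficacy and test significance in an exploratory manner only".

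Under section 7, H2 (knowledge) is read from baseline to month 1. H3 (disclosure experiences) is read "at 1-month follow-up compared to waitlist". H4 (survivor PTSD, stress and relationship quality; supporter stress and relationship quality) is read "at 3-month follow-up compared to waitlist".

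Section 20a also plans the reliable change index with odds ratios, the percentage meeting PCL diagnostic criteria, paired t-tests, and time-by-condition random-effects models. It does not commit to reporting the baseline-to-follow-up correlation, or the raw means and SDs from which these ds could be converted.

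**The concern.** The SD of change scores is not a fixed yardstick. It is small when people keep their rank between visits (high rho) and large when they do not. Two outcomes with the same benefit in raw SD units will show different ds if their correlations differ. The outcomes here are unlike one another (knowledge, disclosure frequency, negative reactions, responsiveness, PTSD, stress, relationship quality), so there is little reason to expect one common rho.

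Rho and the SD may also change during follow-up. Section 18a chose the time points because "recovery occurs most rapidly within the first 3 months post-assault".

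At stake is how the pilot's main efficacy figures are read. A between-group d is usually set against other trials' ds or against customary benchmarks, most of which rest on a raw-score SD. The reader of a change-score d cannot make that comparison without rho or the SDs.

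**Working it through.** **Inputs**

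- Denominator (change-score SD) and construction of the between-group d: section 20a.
- Rho: not in the documents; assumed 0.3 to 0.8.
- k, the ratio of follow-up SD to baseline SD: not in the documents; assumed 1 at first, then 0.8 to 1.5.
- Benefit: an illustrative difference in mean change of 0.40 baseline SD.
- The arms compared are given the same change SD, so that only the effect of the scale shows.

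The plan states no effect size, so there is no figure of its own to reproduce.

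**Step 1. The change SD.** SD_change = SD_baseline × sqrt(1 + k² − 2·rho·k). With k = 1 this is SD_baseline × sqrt(2(1 − rho)).

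**Step 2. The planned between-group d.** It equals the benefit in baseline SDs divided by sqrt(1 + k² − 2·rho·k). For example, with rho = 0.7 and k = 1 the divisor is sqrt(0.6) = 0.775. If CARE changes by 0.9 and waitlist by 0.5 baseline SD, the within-group ds are 1.162 and 0.645, and their difference is 0.516, not 0.40.

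| Assumed rho (k = 1) | Multiplier 1/sqrt(2(1 − rho)) | Planned d for a benefit of 0.40 | d on baseline SD |
|---|---|---|---|
| 0.3 | 0.845 | 0.338 | 0.40 |
| 0.5 | 1.000 | 0.400 | 0.40 |
| 0.7 | 1.291 | 0.516 | 0.40 |
| 0.8 | 1.581 | 0.632 | 0.40 |

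**Step 3. When the two agree.** The planned d equals the baseline-SD d when 1 + k² − 2·rho·k = 1, that is, when rho = k/2. With equal SDs this is rho = 0.5.

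**Step 4. Letting the SD change too.** Over k = 0.8 to 1.5 and rho = 0.3 to 0.8, the lowest value is 0.40/sqrt(1 + 2.25 − 0.90) = 0.40/1.533 = 0.26. The highest is 0.40/sqrt(1 + 0.64 − 1.28) = 0.40/0.60 = 0.67.

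**Step 5. Month 1 against month 3.** Start from rho = 0.7 and k = 1 at month 1 (d = 0.516) and keep the benefit at 0.40.

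| Assumed month-3 values | Planned d | Change |
|---|---|---|
| rho 0.4, k 1 | 0.365 | −29% |
| rho 0.6, k 1 | 0.447 | −13% |
| rho 0.65, k 0.8 | 0.40/sqrt(1.64 − 1.04) = 0.516 | none |
| rho 0.7, k 0.8 | 0.40/sqrt(1.64 − 1.12) = 0.555 | +7% |

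The shift can be down, nil or up, depending on quantities that the documents do not give.

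**The case against.** The change-score d is a recognised effect size. It matches the planned paired t-tests (t = d × sqrt(n)), and 20a states its denominator openly. As a within-group figure it needs no defence, and it should be kept.

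The planned contrast is between arms on one outcome at one visit. If one change SD serves all arms, rho rescales every arm alike, and neither the sign nor the ordering of the arms is affected. That also stands: on this footing the problem is one of size and comparability, not of direction.

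A reader might infer that month-3 ds will shrink against month-1 ds, or that a planned comparison over time is spoiled. The documents support neither. Section 7 assigns different outcomes to the two visits, no hypothesis follows one outcome from month 1 to month 3, and Step 5 shows that the direction of any shift is unknown. A reader might also infer that every d in the plan is affected. The H1 acceptability d is not: acceptability is rated at month 1 and no baseline rating is described, so a change-score SD cannot apply.

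The ds are not the only efficacy evidence. The reliable-change odds ratios, diagnostic percentages and random-effects models do not use this scale. But none of them supplies a d on the raw-score scale.

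Finally, sampling error is large. With 60–72 dyads in three arms (20–24 per arm) and complete data, the approximate 95% half-width for a between-group d is 1.96 × sqrt(2/20) = 0.62 to 1.96 × sqrt(2/24) = 0.57. That exceeds the spread of 0.632 − 0.338 = 0.29 in the first table. This limits the practical weight of the point. It does not remove it, because the scale effect is systematic and an interval around the planned d does not show it.

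**Conclusion.** The point holds for the between-group ds under H2–H4. Their size mixes benefit with rho and with any change in SD, and they are not directly comparable with other trials' ds, or across outcomes or visits. They can be converted once rho or the raw SDs are known, but the plan does not commit to reporting these.

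A benefit of 0.40 baseline SD would read 0.34 to 0.63 over assumed rho of 0.3 to 0.8 with equal SDs, and 0.26 to 0.67 if the SD ratio may also range from 0.8 to 1.5. All of these rho and SD ratios are assumptions. The algebra is not.

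This is a worthwhile, inexpensive improvement to how effects are reported. It is not an error that harms the data or invalidates the other planned analyses.

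**What to change.** Amend 20a along these lines:

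> For H2–H4, the between-group d is the difference between conditions in mean change from baseline, divided by the baseline SD of that outcome pooled over the three arms, calculated separately for survivors and supporters and used unchanged at every follow-up. The within-group d (mean change divided by the SD of change scores) is reported as a separate, labelled figure. Raw mean changes, baseline and change SDs, and the baseline-to-follow-up correlation are reported for each outcome.

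The H1 acceptability d lies outside this change and needs its own short definition.

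The cost is a few sentences in 20a and some extra table columns. No new data are needed, and the t-tests and models are unchanged.

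Two limits of the baseline SD should be stated with the results:

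- For survivor PTSD it may be narrow, because section 10 requires a screening score of 2/5 or above. This would inflate that d.
- For H3 reactions it may be a poor yardstick, because section 10 admits survivors who have not yet told the supporter but were already planning to. For them a baseline reaction may be absent or at the floor of the scale.

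Reporting the raw changes and SDs lets a reader allow for both.
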